Study Title: *Clinical Study of the CO₂RE Laser Device for Treatment of Vulvar Lichen Sclerosus*

Protocol Number: DHF25211

IRB Revision Date: February 19, 2019

NCT#: NCT04148651

Study Type: Prospective Clinical Study

Device: *CO₂RE Laser*

Sponsored By: Candela Corporation
[name]
[name]

This document is the property of **Candela Corporation** No part of this document may be reproduced, stored in retrieval system, or transmitted in any form or any means, electronic, mechanical, photocopying, recording or otherwise without prior written permission from **Candela Corporation**.

TABLE 1- STUDY SYNOPSIS

Short study name	Vulvar Lichen Sclerosus Treatment with CO ₂ RE			
Proprietary name	Syneron Candela CO ₂ RE Laser			
Intended Use	The CO ₂ RE laser system is a fractional CO ₂ laser that is FDA-cleared under a 510(k) K151655 for laser incision, excision, ablation and/or vaporization and of soft tissue in gynecology (GYN).			
Design	Prospective, non-randomized, single group assignment, interventional clinical trial			
Study Population	Up to 45 female subjects from up to four investigational sites, age 18-80 years			
Sites and Investigators	Up to 4 investigational sites			
Treatment Duration	
Eligible subjects, with a diagnosis of vulvar lichen sclerosus (VLS) supported by histologic findings on biopsy and/or clinical signs on physical examination and recalcitrant to mid- to high-potency steroid therapy, will undergo up to 5 treatments at 4±1-week intervals to the vulva with the CO₂RE device and External Intima disposable handpiece. Up to 10 subjects will have a biopsy taken at the baseline visit, at the 6-week follow-up and at the 6-month follow-up to evaluate histological markers compared to pre-treatment biopsy findings.
 
A 1 week ± 2 days post first treatment phone call by a study nurse for safety evaluation will be performed.
 
Subjects will return for 4 follow-up (FU) visits: at 6 weeks, 3 months, 6 months and 12 months after the final treatment.
 
Methodology described in protocol to evaluate efficacy of treatments will be carried out at each visit at the clinic.
			
Primary Objective	Evaluate the efficacy of a series of CO ₂ RE treatments to improve the symptoms, clinical signs, and architectural changes associated with vulvar lichen sclerosus, at 6 weeks, 3 months, 6 months and 12 months after the final treatment.			

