The CO₂RE system device is FDA-cleared under a 510(k) K151655 - intended for laser incision, excision, ablation, and/or vaporization of soft tissue in gynecology (GYN) for the treatment of: conization of the cervix, including cervical intra-epithelial neoplasia (CIN) and vulvar and vaginal intra-epithelial neoplasia (VIN, VAIN); condyloma acuminata, including cervical, genital, vulvar, perineal, and Bowen's disease (Erythroplasia of Queyrat) and Bowenoid papulosa (BP) lesions; and leukoplakia (vulvar dystrophies).

STUDY DESIGN

Study Duration and Timelines

This study is a prospective, non-randomized, single group assignment, interventional clinical trial to evaluate the CO₂RE laser device for safety and efficacy for vulvar lichen sclerosus (vulvar dystrophy) treatment.

Up to a total of 45 female candidates, seeking treatment for vulvar lichen sclerosus from the participating investigator will be enrolled at a participating study site. Subjects will receive up to five (5) CO₂RE treatments.

A 1-week post first treatment safety call will be performed by a study nurse to review the patient daily diary.

Each subject will be followed for 4 additional post treatment visits (FU visits) that will be conducted at:

- 6 weeks post last treatment – 6wk FU ± 2 weeks (Efficacy & Safety).
- 3 months post last treatment – 3m FU ± 2 weeks (Efficacy & Safety).
- 6 months post last treatment – 6m FU ± 2 weeks (Efficacy & Safety).

- 12 months post last treatment – 12m FU ± 2 weeks (Efficacy & Safety).

STUDY OBJECTIVES AND END POINTS

Primary Objective

To evaluate the efficacy of a series of CO₂RE treatments to improve the symptoms, clinical signs, and architectural changes associated with vulvar lichen sclerosus, at 6 weeks, 3 months, 6 months and 12 months after the final treatment.

Secondary Objectives

1. Evaluate sexual function at the 3-month and 6-month follow-ups compared to baseline.
2. Evaluate histological markers at the 6-week and 6-month follow-up compared to baseline.
3. Evaluate discomfort following each treatment.
4. Evaluate the safety of CO₂RE treatments for VLS during the study.
5. Evaluate subject satisfaction at the 6-week, 3-month, 6-month and 12-month follow-up visits.

Primary Endpoint

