Change from baseline in presence and severity of symptoms (5-point severity scale), clinical signs (3-point severity scale) and architectural changes (3-point severity scale) at the 6-week, 3-month, 6-month and 12-month follow-up visits. (**Appendices I & II**).

Secondary Safety Endpoints

Evaluate the safety of the treatment:

1. Clinical evaluation of treated area at each study visit. Clinical photography will be performed for study documentation (**Appendix IV**).
2. Pain/discomfort level using a 10-point Numerical Scale Response (NSR) after each treatment (**Appendix V**).
3. Number, severity and type of adverse events recorded throughout course of the study.
4. 1 week ± 2 days post first treatment safety phone call (review of 1-week patient diary) – (**Appendix VI**).

Secondary Efficacy Endpoints

1. Sexual function, using the Female Sexual Function Index (**Appendix III**), at baseline and at the 3-month and 6-month follow-ups. *An overall score ≤ 26.55 is classified as Female Sexual Disorder (FSD).*¹⁵
2. Histological signs (degree of hyperkeratosis, epidermal atrophy and dermal inflammation) at baseline and at 6 weeks and 6 months after the final treatment.
3. Subject satisfaction, using a 5-point Likert scale (-2=very dissatisfied; 2=Very satisfied), will be assessed at the 6-week, 3-month, 6-month and 12-month follow-up visits (**Appendix VII**).

SUBJECT POPULATION

Up to 45 female subjects who meet the following inclusion / exclusion criteria may be enrolled.

Subject Withdrawal and Replacement

Subjects enrolled in the study can discontinue their participation at any time for any reason without prejudice or reduction in the quality of their medical care. The investigator or sponsor can terminate a subject's participation in this study to protect the subject's health or if the subject fails to follow directions resulting in noncompliance to study procedures. Subjects who withdraw or are terminated from the study may be replaced to allow up to 45 subjects to complete the study. Subjects who fail to complete the treatment will be replaced and will not be evaluable.

Inclusion Criteria

1. Able to read, understand and sign informed consent for study participation;
2. Female subjects with age 18-80 years;
3. Biopsy demonstrates biopsy-proven lichen sclerosus and/or there are characteristic changes for vulvar lichen sclerosus on physical examination;

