Following the first treatment:

1. Subjects will receive a daily diary, which they will be requested to complete, regarding their comfort and any adverse events for the 7-day period following treatment.

Following each treatment session

1. If the subject experiences itch or discomfort after treatment, ice packs may be applied to the treatment area.
2. Temporary erythema (redness) and edema (swelling), as well as heat and tightening sensations, may occur up to a few hours after the treatment. If the subject feels significant discomfort longer than a few hours, an over-the-counter pain medication such as Tylenol® (Acetaminophen) may be used. Nonsteroidal anti-inflammatory drugs (NSAID), such as aspirin, Ibuprofen (Advil, Motrin), naproxen (Aleve, Anaprox, Naprelan, Naprosyn), etc. should be avoided unless the patient does not experience symptomatic relief with or is contraindicated to acetaminophen.
3. On the evening after the treatment, subjects should wash the treated areas gently with lukewarm water and avoid very hot or cold water in these areas. Generally, subjects may use their regular cleanser after treatment, as long as these are not mechanical scrubs or exfoliants.
4. Subject should refrain from sexual activities for a period of 7 days.
5. Any pain, fever or unusual discharge should be immediately reported.

 Candela Corporation Confidential	Clinical Study of the CO₂RE Laser Device for Treatment of Vulvar Lichen Sclerosus				
	Protocol #	DHF25211	Rev. Date	February 19, 2019	Page 16 of 39

Follow-up Visits

1. All subjects will be requested to return to the clinic at the following time-points during the study to assess the clinical safety and performance of the device:
 - 6 weeks post last treatment – 6wk FU ± 2 weeks.
 - 3 months post last treatment – 3m FU ± 2 weeks.
 - 6 months post last treatment – 6m FU ± 2 weeks.
 - 12 months post last treatment – 12m FU ± 2 weeks.
2. At the follow-up visits, the following assessments will be performed, and data recorded:
 - Review changes in medication, medical history and AE, if applicable, from last visit.
 - Photographs of treated area.
 - Optional biopsy of treated area (6-week and 6-month follow-up only).
 - Subject assessment of symptom severity.
 - Investigator assessment of clinical signs.
 - Subject Satisfaction.

DATA ANALYSIS

Recording

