All data will be recorded on Case Report Forms (CRFs) or transcribed from source documentation, where applicable (i.e. lab reports). The site will be monitored by Syneron Candela staff or designees to assure adherence to the clinical trial requirements, subject safety, protocol procedures, and for data accuracy. The Case Report Forms and images will be reviewed and retrieved during the monitoring visit. All source documentation will remain in the subject's files at the site.

Review and Analysis of all data collected will be conducted by the Sponsor or designee as described for this protocol with the following data:

Demography and Baseline Measurements

Demographic and baseline/screening measurements (e.g., age, weight, clinical VLS signs and digital images) will be collected and descriptively presented.

Treatment Visits

Clinical VLS signs as assessed by the study investigator, photographs of the treated region, and NSR scores will be collected and compared to baseline to assess efficacy and safety. Any potential adverse events will be documented.

Follow-up Visit Measurements

Follow-up measurements, efficacy and satisfaction assessment scores, and digital images will be used for comparative measurements with their respective data at baseline. Primary endpoints will be evaluated at the 6-week, 3-month, 6-month and 12-month follow-up visit.

Safety

Safety of device procedure will be evaluated throughout the study. Any side effects to the treated area will be reported by the subject, the study investigator and the research staff. The occurrence and severity of all complications from the start of the study will be recorded.

ADVERSE EVENTS (AE)

An adverse event (AE) is any adverse change in health or side effect that occurs in a study participant during their participation in the study.

Anticipated Adverse Effects

An adverse event (AE) is any undesired clinical occurrence in a study subject as indicated by signs, symptoms, illnesses, events that develop or worsen in severity in association with the study when deemed by the Investigator to be related to use of the device or study procedures.

Anticipated post-treatment adverse effects which could result from the CO₂RE treatment include pain, swelling, bruising (ecchymosis), blistering, burn, and infection.

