The Investigator will document all adverse signs and symptoms regardless of severity or frequency that are either volunteered by subjects or observed during the course of the study that are related to the device. The Investigator will also record adverse experiences of subjects resulting from concurrent illnesses, reactions to concurrent medications, or progression of disease states that the Investigator deems related to the device. Included in the description will be the nature of the sign or symptom, the date of onset, whether the event was serious, the severity, the relationship to study procedures or investigational device, the action taken, the date of resolution, and the outcome. The Principal Investigator will determine the relationship of the adverse device effect to the investigational device.

Unanticipated Adverse Device Effects

For device studies, part 21 CRF 812.3(s) uses the term unanticipated adverse device effect which is defined as any serious adverse effect on health or safety or any life-threatening problem or death caused by, or associated with, a device, if that effect, problem, or death was not previously identified in nature, severity, or degree of incidence in the investigational plan or application (including a supplementary plan or application), or any other unanticipated serious problem associated with a device that relates to the rights, safety, or welfare of subjects.

All unanticipated adverse effects will be graded as follows:

Mild: Sign or symptom, usually transient, non-life-threatening requiring no special treatment and generally not interfering with usual activities.

Moderate: Sign or symptom, non-life-threatening which may be ameliorated by simple therapeutic measures and may interfere with usual activity.

Severe: Sign or symptom that is intense or debilitating but non-life-threatening and that interferes with usual activities. Recovery is usually aided by therapeutic measures and the discontinuation of the study device may be required.

Serious: Any untoward medical occurrence that at any time results in death or life-threatening illness, resulting in persistent or significant disability/incapacity.

The relationship of the adverse effect to the study is defined as follows:

Probable: An adverse event has a strong temporal relationship to study device, and another etiology is unlikely or significantly less likely.

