Subjects may or may not benefit from improvement in lichen sclerosus. All subjects in the study are expected to have some benefit from the treatment procedures. Subject will receive treatment procedures at no cost. This study will benefit the advancement of medicine by generating data on safety and efficacy that will aid in the development of an alternative treatment options to ultra-potent topical corticosteroids (such as clobetasol propionate). This study will benefit the advancement of medicine by generating data on safety and efficacy that will aid in the development of an alternative or adjunctive treatment option for female patients who do not improve with topical corticosteroid use for vulvar lichen sclerosus.

 Candela Corporation Confidential	Clinical Study of the CO₂RE Laser Device for Treatment of Vulvar Lichen Sclerosus				
	Protocol #	DHF25211	Rev. Date	February 19, 2019	Page 21 of 39

Payment for Participation

Subjects will be paid a total of up to \$200 for up to 10 study visits (\$20 per visit) for all study visits and evaluations. Subjects will not pay for office visits, examinations or procedures that are part of this clinical study. Subjects who do not complete all study-related procedures and requirements will receive partial payments according to the treatment and follow-up visits that were completed (\$20 per visit). Subjects who are biopsied at baseline, at the 6-week follow-up and the 6-month follow-up will receive an additional \$200 (~\$67 per visit). Payments will be issued upon study completion.

ETHICS AND GOOD CLINICAL PRACTICE

This study will be carried out in compliance with the following:

- Syneron Candela's Standard Operating Procedures (SOPs).
- Declaration of Helsinki (current version).
- US Code of Federal Regulations (Title 21CFR including parts 50, 56 and 812 governing informed consent and IRB regulations).
- International Conference on Harmonization (ICH) Harmonized Tripartite Guideline for Good Clinical Practice (GCP), 1996.

QUALITY ASSURANCE AND STUDY MONITORING

Study Monitoring/Auditing/Inspection

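### Treated women who do not complete treatment are replaced and excluded as not evaluable, so efficacy will describe completers only and improvement is likely to be overstated

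*Protocol*

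**What the plan says.** The rule is in the Protocol, SUBJECT POPULATION, Subject Withdrawal and Replacement: "Subjects who fail to complete the treatment will be replaced and will not be evaluable". It carries no condition on the reason for stopping or on the number of sessions received. The sentence before it says that withdrawn or terminated subjects "may be replaced to allow up to 45 subjects to complete the study". The same paragraph lets a subject leave for any reason, and lets the investigator or sponsor end her participation for her health or for noncompliance.

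Other sections bear on the rule:

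- Table 1, Treatment Duration: eligible subjects "will undergo up to 5 treatments at 4±1-week intervals". No section says how many sessions make a complete course.
- Study Duration and Timelines: "Each subject will be followed for 4 additional post treatment visits (FU visits) that will be conducted at" 6 weeks, 3, 6 and 12 months after the last treatment.
- Follow-up Visits: "All subjects will be requested to return to the clinic at the following time-points during the study".
- Payment for Participation: subjects who do not complete everything "will receive partial payments according to the treatment and follow-up visits that were completed".
- Unanticipated Adverse Device Effects, definition of the severe grade: "Recovery is usually aided by therapeutic measures and the discontinuation of the study device may be required".
- DATA ANALYSIS, Safety: "The occurrence and severity of all complications from the start of the study will be recorded".

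The design is a single group, and the primary endpoint is change from baseline in symptoms, signs and architectural changes.

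**The concern.** Completing treatment is something that happens after treatment starts, and it may depend on how treatment is going. A woman who stops because she cannot tolerate the laser, or whose participation is ended for her health, is removed from the efficacy results. Her replacement counts only if she finishes.

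In a single-group trial the change from baseline is the whole efficacy result, and there is no control arm in which the same selection would operate. If stoppers fare worse than finishers, the reported improvement and satisfaction are both too high.

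Two features make this worse. First, because completion is not defined, each case can be decided individually. Table 2 and Appendix II have the investigator score signs before treatments, so at most four post-baseline scores (before sessions 2 to 5) may be known when the decision is made. Second, a woman who stops treatment but stays in the study falls within the follow-up schedule and is paid for the visits she attends. Her outcomes can therefore be collected and then not used.

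**Working it through.** The Protocol states no dropout rate, effect size or standard deviation, so there is no figure of its own to reproduce. The check has two parts.

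**Does any text restore the excluded women?** The follow-up and payment sections allow data to be collected from them. The Follow-up Visit Measurements section says that follow-up scores will be compared with baseline, but names no set that includes non-completers. Safety recording covers complications from the start of the study, but that concerns safety, not efficacy. The exclusion therefore stands as written for every efficacy endpoint. A woman withdrawn or terminated before finishing her course also fails to complete the treatment, so the exclusion reaches her as well.

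**How large could the effect be?** Let d be the proportion of treated women who stop, c the mean improvement in completers and s the mean improvement in stoppers.

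- All-treated mean = (1 − d) × c + d × s
- Overstatement = c − all-treated mean = d × (c − s)

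All three inputs are assumptions. Take c = 1.5 points on one 5-point symptom item of Appendix I, and d = 10%, 20% or 30%. The completer-only report is 1.50 in every row.

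| s (stoppers) | All-treated mean at d = 10% / 20% / 30% | Overstatement |
|---|---|---|
| 0 | 1.35 / 1.20 / 1.05 | 0.15 / 0.30 / 0.45 |
| 1.0 | 1.45 / 1.40 / 1.35 | 0.05 / 0.10 / 0.15 |
| 1.5 | 1.50 / 1.50 / 1.50 | 0 |
| 2.0 | 1.55 / 1.60 / 1.65 | −0.05 / −0.10 / −0.15 |

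Worked cell: d = 0.2 and s = 0 give 0.8 × 1.5 + 0.2 × 0 = 1.20, so the overstatement is 1.50 − 1.20 = 0.30.

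The relative overstatement does not depend on c. With k = s/c it is 1 / ((1 − d) + d × k) − 1:

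- k = 0: 11.1%, 25.0% and 42.9% at d = 10%, 20% and 30%. For example, 1/0.8 − 1 = 25.0%.
- k = 0.5: 5.3%, 11.1% and 17.6%.
- k = 1: zero.

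**The case against.** The strongest reply is that the direction is not established. The Protocol gives no stopping pattern. The phrase about discontinuing the device belongs to a severity definition and is not a stopping rule. Ending participation for health reasons shows a link with safety, not with change in lichen sclerosus symptoms or signs. Noncompliance need not relate to outcome at all. This is fair as far as it goes: direction and size are unproven, and the bias could be zero or reversed. It does not defend the rule, which excludes women without regard to reason and so cannot separate harmless stopping from informative stopping.

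A second reply is that, if fewer than five sessions can be a full course, few women may be excluded. That may prove true, but it depends on a classification that the Protocol does not define.

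Third, the follow-up and payment sections are general. Partial payment also covers women who finish treatment and miss later visits, and women who leave the study altogether provide no data to set aside. This stands: the loss of usable data concerns women who stop treatment and remain in the study.

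Fourth, calling a woman evaluable does not create an outcome for her. All primary assessments fall after the last treatment, and symptoms are not collected between baseline and 6 weeks. This also stands, and it limits what the fix can recover.

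Finally, the study is uncontrolled and states no success threshold, and a completer description does answer part of the question about a series of treatments. That supports keeping completers as a supportive analysis. It does not support making them the only one.

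**Conclusion.** The concern holds and should be fixed. Followed as written, the Protocol selects its efficacy set on a post-treatment event in a trial with no comparator. Existence of the exclusion is certain. Overstatement is the likely direction, because stopping can follow intolerance or termination for health reasons, but it is an inference. The size cannot be known from the Protocol. Under the assumed values above it runs from 0.05 to 0.45 points where stoppers do worse than completers, and is zero or negative otherwise. The rule concerns women who do not finish treatment. It does not address those who finish and then miss follow-up.

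One related point is an ambiguity and not an error: the words not evaluable are not limited to efficacy, although adverse events are collected from everyone.

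**What to change.** Replace the sentence under Subject Withdrawal and Replacement with wording to this effect:

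- Every subject with a baseline assessment who receives at least one CO₂RE treatment is evaluable for efficacy, and all treated subjects stay in the safety analysis.
- Subjects who stop treatment early and agree are asked to attend the scheduled follow-up visits, dated from the last treatment they received.
- The number of subjects who stop, and their reasons, are reported.
- Additional subjects may be enrolled but do not displace those who stopped.
- The completer analysis is supportive, with completion defined for analysis purposes before outcomes are reviewed.

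Sign scores taken before treatment sessions may be described for early stoppers. They do not stand in for the primary follow-up assessments.

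The cost is one paragraph of Protocol wording; the visits and payments already exist. The reported improvement may be somewhat smaller. Some early stoppers will leave entirely, and their missing follow-up will need to be reported and handled in the analysis.
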